9.4.3. Pharmacokinetic Analyses

9.4.3.1. Pharmacokinetic Parameters

Pharmacokinetic analysis will be the responsibility of the Clinical Pharmacology Modeling and Simulation (CPMS) Department, GSK.

Population Pharmacokinetics

Plasma concentration-time data for GSK2879552 from all Arms and Parts may be combined with data from other studies and may be analyzed using a population approach. A nonlinear mixed effects model will be used to determine population PK parameters (absorption rate, K_a , apparent clearance, CL/F and volume of distribution, V/F) and summary exposure measures (e.g. C_{max} , AUC and $C_{av} = AUC/\tau$) and identify relevant covariates (e.g., age, weight, or disease related covariates). Results may be reported separately.

9.4.3.2. Statistical Analysis of Pharmacokinetic Data

Statistical analyses of the PK concentration data will be the responsibility of Discovery Biometrics, GSK.

Plasma concentration-time data for GSK2879552, GSK2879552 metabolite(s) as deemed appropriate, and azacitidine will be listed by dose and arm and summarized using descriptive statistics (n, mean, standard deviation [SD], median, minimum and maximum) by planned relative assessment time. Mean and/ or median values may be plotted over time.

9.4.4. Pharmacokinetic/Pharmacodynamic Analyses

Observed or predicted concentrations will be combined with safety and/or efficacy, measures of interest to examine potential exposure response relationships.

Quantitative safety parameters will be plotted graphically against summary exposure measures (eg; C_{max} , C_{trough} , and C_{av}). Where evidence of a signal is seen, linear and non-linear mixed effect models will be fitted to the data to estimate PK/PD parameters of interest; e.g. slope, baseline (E_0), or exposure producing 50% of the maximum effect (EC_{50}), and maximum effect (E_{max}).

Overall efficacy data may be described using categorical model and/or continuous models with summary exposure parameters (eg; C_{max} , C_{trough} , and C_{av}) as covariates derived from the population PK analysis.

9.4.4.1. Translational Research Analyses

Exploratory analysis may be performed to examine potential relationships between anticancer activity and changes in markers of LSD 1 target inhibition or disease biology or between therapeutic activity and potential markers of sensitivity or resistance.

The results of translational research investigations may be reported separately from the main clinical study report or as an amendment. Endpoints of interest from all comparisons will be descriptively and/or graphically summarized as appropriate to the data. Further details on the translational research analyses will be provided in the RAP.

9.4.4.2. Novel Biomarker(s) Analyses

The results of these biomarker investigations may be reported separately from the main clinical study report. All endpoints of interest from all comparisons will be descriptively and/or graphically summarized as appropriate to the data.

Additional exploratory analyses may be performed to further characterize any novel biomarkers.

10. STUDY GOVERNANCE CONSIDERATIONS

10.1. Posting of Information on Publicly Available Clinical Trial Registers

Study information from this protocol will be posted on publicly available clinical trial registers before enrollment of subjects begins.

10.2. Regulatory and Ethical Considerations, Including the Informed Consent Process

Prior to initiation of a site, GSK will obtain favourable opinion/approval from the appropriate regulatory agency to conduct the study in accordance with ICH Good Clinical Practice (GCP) and applicable country-specific regulatory requirements.

The study will be conducted in accordance with all applicable regulatory requirements, and with GSK policy.

The study will also be conducted in accordance with ICH Good Clinical Practice (GCP), all applicable subject privacy requirements, and the guiding principles of the current version of the Declaration of Helsinki. This includes, but is not limited to, the following:

- IRB/IEC review and favorable opinion/approval of the study protocol and amendments as applicable
- Obtaining signed informed consent
- Investigator reporting requirements (e.g. reporting of AEs/SAEs/protocol deviations to IRB/IEC)
- GSK will provide full details of the above procedures, either verbally, in writing, or both.
- Signed informed consent must be obtained for each subject prior to participation in the study
- The IEC/IRB, and where applicable the regulatory authority, approve the clinical protocol and all optional assessments, including genetic research.
- Optional assessments (including those in a separate protocol and/or under separate informed consent) and the clinical protocol should be concurrently submitted for approval unless regulation requires separate submission.

- Approval of the optional assessments may occur after approval is granted for the clinical protocol where required by regulatory authorities. In this situation, written approval of the clinical protocol should state that approval of optional assessments is being deferred and the study, with the exception of the optional assessments, can be initiated.

10.3. Quality Control (Study Monitoring)

- In accordance with applicable regulations including GCP, and GSK procedures, GSK monitors will contact the site prior to the start of the study to review with the site staff the protocol, study requirements, and their responsibilities to satisfy regulatory, ethical, and GSK requirements.
- When reviewing data collection procedures, the discussion will also include identification, agreement and documentation of data items for which the eCRF will serve as the source document.

GSK will monitor the study and site activity to verify that the:

- Data are authentic, accurate, and complete.
- Safety and rights of subjects are being protected.
- Study is conducted in accordance with the currently approved protocol and any other study agreements, GCP, and all applicable regulatory requirements.

The investigator and the head of the medical institution (where applicable) agrees to allow the monitor direct access to all relevant documents

10.4. Quality Assurance

- To ensure compliance with GCP and all applicable regulatory requirements, GSK may conduct a quality assurance assessment and/or audit of the site records, and the regulatory agencies may conduct a regulatory inspection at any time during or after completion of the study.
- In the event of an assessment, audit or inspection, the investigator (and institution) must agree to grant the advisor(s), auditor(s) and inspector(s) direct access to all relevant documents and to allocate their time and the time of their staff to discuss the conduct of the study, any findings/relevant issues and to implement any corrective and/or preventative actions to address any findings/issues identified.

10.5. Study and Site Closure

- Upon completion or premature discontinuation of the study, the GSK monitor will conduct site closure activities with the investigator or site staff, as appropriate, in accordance with applicable regulations including GCP, and GSK Standard Operating Procedures.

- GSK reserves the right to temporarily suspend or prematurely discontinue this study at any time for reasons including, but not limited to, safety or ethical issues or severe non-compliance. For multicenter studies, this can occur at one or more or at all sites.
- If GSK determines such action is needed, GSK will discuss the reasons for taking such action with the investigator or the head of the medical institution (where applicable). When feasible, GSK will provide advance notification to the investigator or the head of the medical institution, where applicable, of the impending action.
- If the study is suspended or prematurely discontinued for safety reasons, GSK will promptly inform all investigators, heads of the medical institutions (where applicable) and/or institution(s) conducting the study. GSK will also promptly inform the relevant regulatory authorities of the suspension or premature discontinuation of the study and the reason(s) for the action.
- If required by applicable regulations, the investigator or the head of the medical institution (where applicable) must inform the IRB/IEC promptly and provide the reason for the suspension or premature discontinuation.

10.6. Records Retention

- Following closure of the study, the investigator or the head of the medical institution (where applicable) must maintain all site study records (except for those required by local regulations to be maintained elsewhere), in a safe and secure location.
- The records must be maintained to allow easy and timely retrieval, when needed (e.g., for a GSK audit or regulatory inspection) and must be available for review in conjunction with assessment of the facility, supporting systems, and relevant site staff.
- Where permitted by local laws/regulations or institutional policy, some or all of these records can be maintained in a format other than hard copy (e.g., microfiche, scanned, electronic); however, caution needs to be exercised before such action is taken.
- The investigator must ensure that all reproductions are legible and are a true and accurate copy of the original and meet accessibility and retrieval standards, including re-generating a hard copy, if required. Furthermore, the investigator must ensure there is an acceptable back-up of these reproductions and that an acceptable quality control process exists for making these reproductions.
- GSK will inform the investigator of the time period for retaining these records to comply with all applicable regulatory requirements. The minimum retention time will meet the strictest standard applicable to that site for the study, as dictated by any institutional requirements or local laws or regulations, GSK standards/procedures, and/or institutional requirements.
- The investigator must notify GSK of any changes in the archival arrangements, including, but not limited to, archival at an off-site facility or transfer of

ownership of the records in the event the investigator is no longer associated with the site.

10.7. Provision of Study Results to Investigators, Posting of Information on Publically Available Clinical Trials Registers and Publication

Where required by applicable regulatory requirements, an investigator signatory will be identified for the approval of the clinical study report. The investigator will be provided reasonable access to statistical tables, figures, and relevant reports and will have the opportunity to review the complete study results at a GSK site or other mutually-agreeable location.

GSK will also provide the investigator with the full summary of the study results. The investigator is encouraged to share the summary results with the study subjects, as appropriate.

The procedures and timing for public disclosure of the results summary and for development of a manuscript for publication will be in accordance with GSK Policy.

12. APPENDICES

12.1. Appendix 1: Abbreviations and Trademarks

Abbreviations

| | |
|------------------|---|
| AE(s) | Adverse Event(s) |
| AML | Acute Myeloid Leukemia |
| ALP | Alkaline Phosphatase |
| ALT | Alanine aminotransferase |
| ANC | Absolute Neutrophil Count |
| aPTT | Activated Partial Thromboplastin Time |
| AST | Aspartate aminotransferase |
| ATRA | All-Trans Retinoic Acid |
| AUC(0-∞) | Area under the concentration-time curve from time zero (pre-dose) extrapolated to infinite time |
| AUC(0-t) | Area Under the Concentration-time curve from time zero (pre-dose) to last time of quantifiable concentration within a subject |
| AUC(0-τ) | Area Under the Concentration-time curve over the dosing interval |
| β-HCG | Beta-Human Chorionic Gonadotropin |
| BUN | Blood Urea Nitrogen |
| C _{av} | Average concentration |
| CBC | Complete Blood Count |
| CfDNA | Circulating cell free DNA |
| CKD-EPI equation | The Chronic Kidney Disease Epidemiology collaboration equation |
| CL/F | Apparent clearance following oral dosing |
| C _{max} | Maximum observed concentration |
| C _{min} | Minimum observed concentration |
| C _τ | Pre-dose (trough) concentration at the end of the dosing interval |
| CO ₂ | Carbon dioxide |
| CoREST | CoRepressor for Element-1-Silencing Transcription factor |
| CPMS | Clinical Pharmacokinetic Modeling and Simulation |
| CR | Complete Response |
| CRM | Continual Reassessment Method |
| CT | Computed Tomography |
| CV | Coefficient of Variance |
| DAC | 5-Aza-2'-deoxycytidine |
| DHEA | Dehydroepiandrosterone |
| DILI | Drug Induced Liver Injury |
| DLT | Dose-Limiting Toxicity |
| DMPK | Drug Metabolism and Pharmacokinetics |
| DNA | Deoxyribonucleic acid |
| EC | Ethics Committee |
| EC ₅₀ | Half maximal effective concentration |
| ECG(s) | Electrocardiogram(s) |

| | |
|--------|---|
| ECHO | Echocardiogram |
| ECOG | Eastern Cooperative Oncology Group |
| eCRF | Electronic Case Report Form |
| FACTS | Fixed and Adaptive Clinical Trial Simulator |
| FSH | Follicle Stimulating Hormone |
| FTIH | First Time In Humans |
| GCP | Good Clinical Practice |
| GFR | Glomerular Filtration Rate |
| GGT | Gamma Glutamyl Transferase |
| GI | Gastrointestinal |
| GLP | Good Laboratory Practices |
| GSK | GlaxoSmithKline |
| GVHD | Graft-versus-Host-Disease |
| H3K4 | Histone H3 lysine 4 |
| HBV | Hepatitis B Virus |
| HCV | Hepatitis C Virus |
| HDACs | Histone Deacetylases |
| Hgb | Hemoglobin |
| HIV | Human Immunodeficiency Virus |
| h/hr | Hour(s) |
| HLA | Human Leukocyte Antigen |
| HMA | Hypomethylating Agent |
| HPLC | High-Performance Liquid Chromatography |
| HNSTD | Highest Non- Severely Toxic Dose |
| HRT | Hormone Replacement Therapy |
| IB | Investigator's Brochure |
| ICH | International Conference on Harmonization |
| IDSL | International Data Standards Library |
| IgM | Immunoglobulin M |
| IND | Investigational New Drug |
| INR | International Normalization Ratio |
| IP | Investigational Product |
| IPSS-R | The Revised International Prognostic Scoring System |
| IRB | Institutional Review Board |
| IU | International Unit |
| IV | Intravenous |
| IWG | International Working Group |
| Ka | Absorption rate |
| kg | Kilogram |
| L | Liter |
| LFTs | Liver Function Tests |
| LLN | Lower Limit of Normal |
| ln | Naperian (natural) logarithm |
| LSD1 | Lysine Specific Demethylase 1 |
| LSLV | Last Subject's Last Visit |
| LVEF | Left Ventricular Ejection Fraction |

| | |
|-----------|--|
| MATE-1 | Multidrug And Toxin Extrusion Transporter 1 |
| uM | Micromole |
| MCH | Mean Corpuscular Hemoglobin |
| MCHC | Mean Corpuscular Hemoglobin Concentration |
| MCV | Mean Corpuscular Volume |
| MDS | Myelodysplastic syndromes |
| MedDRA | Medical Dictionary for Regulatory Activities |
| mg | Milligrams |
| mL | Milliliter |
| MOCA | Montreal Cognitive Assessment |
| MPV | Mean Platelet Volume |
| MRI | Magnetic Resonance Imaging |
| MSDS | Material Safety Data Sheet |
| msec | Milliseconds |
| MTD | Maximum Tolerated Dose |
| MUGA | Multigated (radionuclide) angiogram |
| NCI-CTCAE | National Cancer Institute - Common Terminology Criteria for Adverse Events |
| N-CRM | The Neuenschwander -Continuous Reassessment Method |
| ng | Nanogram |
| nM | Nanomole |
| NOAEL | No Observed Adverse Effect Level |
| NSAIDs | Non-Steroidal Anti-Inflammatory Drug |
| NYHA | New York Heart Association |
| PARP | poly ADP ribose polymerase |
| PCI | Potential Clinical Importance |
| PCR | Polymerase Chain Reaction |
| PD | Progressive Disease or Pharmacodynamic |
| PK | Pharmacokinetic |
| PR | Partial Response |
| PT | Prothrombin Time |
| PTS | Platform Technology and Science |
| PTT | Partial Thromboplastin Time |
| QTc | Corrected QT interval duration |
| QTcF | QT interval corrected for heart rate by Fridericia's formula |
| RAP | Reporting and Analysis Plan |
| RBC | Red Blood Cells |
| RNA | Ribonucleic acid |
| Ro | Accumulation ratio |
| RP2D | Recommended Phase 2 Dose |
| SAE | Serious Adverse Event(s) |
| sc | subcutaneous |
| SCLC | Small Cell Lung Cancer |
| SD | Standard Deviation |
| SPM | Study Procedures Manual |
| STD | Severely Toxic Dose |

| | |
|------------------|---|
| t | Time of last observed quantifiable concentration |
| t _{1/2} | Terminal phase half-life |
| τ | Dosing interval |
| λ_z | Apparent terminal phase elimination rate constant |
| t _{max} | Time of occurrence of C _{max} |
| ULN | Upper Limit of Normal |
| US/USA | United States/United States of America |
| V/F | Apparent Volume of distribution following oral dosing |
| WBC | White Blood Cells |
| WHO | World Health Organization |

Trademark Information

| |
|---|
| Trademarks of the GlaxoSmithKline group of companies |
| NONE |

| |
|---|
| Trademarks not owned by the GlaxoSmithKline group of companies |
| None |

12.2. Appendix 2: Liver Safety Required Actions and Follow up Assessments

Phase I/II liver chemistry stopping and increased monitoring criteria have been designed to assure subject safety and evaluate liver event etiology (in alignment with the FDA premarketing clinical liver safety guidance).

<http://www.fda.gov/downloads/Drugs/GuidanceComplianceRegulatoryInformation/Guidances/UCM174090.pdf>.

Phase I/II liver chemistry stopping criteria and required follow up assessments

| Liver Chemistry Stopping Criteria – Liver Stopping Event | |
|---|--|
| ALT-absolute | ALT ≥ 5xULN |
| ALT Increase | ALT ≥ 3xULN persists for ≥4 weeks |
| Bilirubin^{1,2} | ALT ≥ 3xULN and bilirubin ≥ 2xULN (>35% direct bilirubin) |
| INR² | ALT ≥ 3xULN and INR>1.5, if INR measured |
| Cannot Monitor | ALT ≥ 3xULN and cannot be monitored weekly for 4 weeks |
| Symptomatic³ | ALT ≥ 3xULN associated with symptoms (new or worsening) believed to be related to liver injury or hypersensitivity |
| Required Actions and Follow up Assessments following Liver Stopping Event | |
| Actions | Follow Up Assessments |
| 
 • Immediately discontinue study treatment • Report the event to GSK within 24 hours • Complete the liver event CRF and complete an SAE data collection tool if the event also meets the criteria for an SAE² • Perform liver event follow up assessments • Monitor the subject until liver chemistries resolve, stabilize, or return to within baseline (see MONITORING below) • Do not restart/rechallenge subject with study treatment unless allowed per protocol and GSK Medical Governance approval is granted (refer to Appendix | 
 • Viral hepatitis serology⁴ • Blood sample for pharmacokinetic (PK) analysis, obtained approximately 48h after last dose⁵ • Serum creatine phosphokinase (CPK) and lactate dehydrogenase (LDH). • Fractionate bilirubin, if total bilirubin≥2xULN • Obtain complete blood count with differential to assess eosinophilia • Record the appearance or worsening of clinical symptoms of liver injury, or hypersensitivity, on the AE report form • Record use of concomitant medications on the concomitant medications report form including acetaminophen, herbal remedies, other over the counter medications |

| | |
|---|---|
| 
3 for more details)
 
 If restart/rechallenge is not granted, permanently discontinue study treatment and may continue subject in the study for any protocol specified follow up assessments 
MONITORING:
 
For bilirubin or INR criteria:
 
 Repeat liver chemistries (include ALT, AST, alkaline phosphatase, bilirubin) and perform liver event follow up assessments within 24 hrs Monitor subjects twice weekly until liver chemistries resolve, stabilize or return to within baseline A specialist or hepatology consultation is recommended 
For All other criteria:
 
 Repeat liver chemistries (include ALT, AST, alkaline phosphatase, bilirubin) and perform liver event follow up assessments within 24-72 hrs Monitor subjects weekly until liver chemistries resolve, stabilize or return to within baseline | 
 Record alcohol use on the liver event alcohol intake case report form 
For bilirubin or INR criteria:
 
 Anti-nuclear antibody, anti-smooth muscle antibody, Type 1 anti-liver kidney microsomal antibodies, and quantitative total immunoglobulin G (IgG or gamma globulins). Serum acetaminophen adduct high pressure liquid chromatography (HPLC) assay (quantifies potential acetaminophen contribution to liver injury in subjects with definite or likely acetaminophen use in the preceding week [James, 2009]). Liver imaging (ultrasound, magnetic resonance, or computerised tomography) and /or liver biopsy to evaluate liver disease: complete Liver Imaging and/or Liver Biopsy CRF forms. |
|---|---|

- Serum bilirubin fractionation should be performed if testing is available. If serum bilirubin fractionation is not immediately available, discontinue study treatment for that subject if ALT \geq 3xULN **and** bilirubin \geq 2xULN. Additionally, if serum bilirubin fractionation testing is unavailable, **record presence of detectable urinary bilirubin on dipstick**, indicating direct bilirubin elevations and suggesting liver injury.
- All events of ALT \geq 3xULN **and** bilirubin \geq 2xULN (>35% direct bilirubin) or ALT \geq 3xULN **and** INR>1.5, if INR measured which may indicate severe liver injury (possible 'Hy's Law'), **must be reported as an SAE (excluding studies of hepatic impairment or cirrhosis)**; INR measurement is not required and the threshold value stated will not apply to subjects receiving anticoagulants
- New or worsening symptoms believed to be related to liver injury (such as fatigue, nausea, vomiting, right upper quadrant pain or tenderness, or jaundice) or believed to be related to hypersensitivity (such as fever, rash or eosinophilia)
- Includes: Hepatitis A IgM antibody; Hepatitis B surface antigen and Hepatitis B Core Antibody (IgM); Hepatitis C RNA; Cytomegalovirus IgM antibody; Epstein-Barr viral capsid antigen IgM antibody (or if unavailable, obtain heterophile antibody or monospot testing); Hepatitis E IgM antibody
- Record the date/time of the PK blood sample draw and the date/time of the last dose of study treatment prior to blood sample draw on the CRF. If the date or time of the last dose is unclear, provide the subject's best approximation. If the date/time of the last dose cannot be approximated OR a PK sample cannot be collected in the time period indicated above, do not obtain a PK sample. Instructions for sample handling and shipping are in the SRM.

Phase I/II Oncology liver chemistry increased monitoring criteria with continued therapy

| Liver Chemistry Increased Monitoring Criteria – Liver Monitoring Event | |
|--|---|
| Criteria | Actions |
| 
ALT \geq3xULN but $<$5xULN and bilirubin $<$2xULN, without symptoms believed to be related to liver injury or hypersensitivity and who can be monitored weekly for 4 weeks
 | 
 • Notify the GSK medical monitor within 24 hours of learning of the abnormality to discuss subject safety. • Subject can continue study treatment • Subject must return weekly for repeat liver chemistries (ALT, AST, alkaline phosphatase, bilirubin) until they resolve, stabilise or return to within baseline¹ • If at any time subject meets the liver chemistry stopping criteria, proceed as described above • If, after 4 weeks of monitoring, ALT $<$3xULN and bilirubin $<$2xULN, monitor subjects twice monthly until liver chemistries normalize or return to within baseline. |

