5.4.1. Liver Chemistry Stopping Criteria

Liver chemistry stopping and increased monitoring criteria have been designed to assure subject safety and evaluate liver event etiology (in alignment with the FDA premarketing clinical liver safety guidance).
<http://www.fda.gov/downloads/Drugs/GuidanceComplianceRegulatoryInformation/Guidances/UCM174090.pdf>

See [Figure 2](#) for liver stopping criteria algorithm.

Figure 2 Liver Chemistry Stopping and Increased Monitoring Algorithm

See [Appendix 2](#) for Liver Safety Required Actions and Follow up Assessments.

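### As Appendix 2 is worded, a first-detected asymptomatic ALT of 3 to <5xULN with bilirubin ≥2xULN and a known direct fraction ≤35% meets neither the stopping nor the increased-monitoring criteria, so the 24-hour medical-monitor notice is not triggered

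*Protocol*

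**What the plan says.** Appendix 2 sorts a subject with raised ALT through two tables.

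- **Stopping.** Six rows: ALT ≥5xULN; "ALT ≥ 3xULN persists for ≥4 weeks"; ALT ≥3xULN with "bilirubin ≥ 2xULN (>35% direct bilirubin"); ALT ≥3xULN with INR above 1.5, if measured; ALT ≥3xULN in a subject who "cannot be monitored weekly for 4 weeks"; and ALT ≥3xULN with liver or hypersensitivity symptoms. Footnote 1 also stops treatment at ALT ≥3xULN and bilirubin ≥2xULN if fractionation is not immediately available. The actions include "Report the event to GSK within 24 hours".
- **Increased monitoring.** ALT ≥3xULN "but $<$5xULN and bilirubin $<$2xULN, without symptoms believed to be related to liver injury or hypersensitivity", in a subject who can be seen weekly for 4 weeks. The actions are "Notify the GSK medical monitor within 24 hours of learning of the abnormality to discuss subject safety", continued treatment and weekly repeat chemistries until values resolve, stabilise or return to within baseline. The step-down line reads "If, after 4 weeks of monitoring, ALT $<$3xULN and bilirubin $<$2xULN, monitor subjects twice monthly".

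Section 5.4.1 also refers to Figure 2, the "Liver Chemistry Stopping and Increased Monitoring Algorithm", which is not reproduced in the text available. Section 5.1, footnote a, admits subjects with isolated bilirubin above 1.5xULN if the direct fraction is below 35% or Gilbert's syndrome is diagnosed. It sets no upper limit on bilirubin.

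**The concern.** The two tables test bilirubin differently. The stopping row asks for a total and a fraction; the monitoring row asks only for a total. Sparing subjects with mainly indirect bilirubin from a mandatory stop is reasonable. Nothing in the visible text explains why the same subjects should also fall outside the monitoring criterion.

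The consequence runs the wrong way for a safety rule: at the same ALT, a higher bilirubin removes a stated safeguard. The case is foreseeable, because eligibility admits subjects with indirect hyperbilirubinaemia and requires ALT ≤2.5xULN at entry. An on-study ALT rise in such a subject is enough to reach it. Section 4.11.1 lists liver-test monitoring and stopping rules among the mitigations for azacitidine hepatotoxicity, so those rules should classify every subject with ALT ≥3xULN.

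**Working it through.** This is a check of logic; the plan states no figure to reproduce.

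**Step 1: one subject, only bilirubin varied.** Take ALT 4xULN, INR 1.0, no symptoms, under 4 weeks' duration, weekly monitoring possible. The ALT, persistence, INR, cannot-monitor and symptom rows are then all unmet, so bilirubin decides.

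| Total bilirubin | Direct fraction | Stopping row or footnote 1 | Monitoring criterion | Result |
|---|---|---|---|---|
| 1.9xULN | 20% or 50% | not met | met | monitor, notice in 24 hours |
| 2.2xULN | 50% | met | not met | stop, report in 24 hours |
| 2.2xULN | not available | met (footnote 1) | not met | stop, report in 24 hours |
| 2.2xULN | 20% or 35% | not met | not met | neither |

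**Step 2: is this the only gap?** The six stopping rows, footnote 1 and the monitoring criterion were applied to every combination of:

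- ALT 3, 4, 4.9, 5xULN
- bilirubin 1, 1.9, 2, 4xULN
- direct fraction unavailable, 20, 35, 36, 60%
- INR 1.0, 1.5, 1.6
- symptoms, weekly monitoring possible and persistence ≥4 weeks, each yes or no

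That is 4 × 4 × 5 × 3 × 2 × 2 × 2 = 1,920 combinations. Of these, 24 meet neither table: ALT 3, 4 or 4.9 (3) × bilirubin 2 or 4 (2) × direct 20 or 35% (2) × INR 1.0 or 1.5 (2) = 24, all without symptoms, monitorable and under 4 weeks. An unmeasured INR behaves like ≤1.5, because the INR row applies only if INR is measured. Every other combination lands in a table with a 24-hour contact. The 24 reflect the grid chosen and say nothing about frequency.

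**Step 3: does other visible text supply what is missing?**

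- Section 7.3.9 asks for significantly abnormal tests to be repeated but gives no interval. It brings in the sponsor only if values fail to normalise within a time the investigator finds reasonable.
- The liver-specific serious-event criterion in Section 12.5.2 also needs more than 35% direct when the fraction is known.
- The Time and Events tables draw chemistry on Days 1, 7, 15 and 22 of cycle 1, then on Day 1 of each 28-day cycle.
- The cannot-monitor and persistence rows have no bilirubin condition. A site can apply them only by planning repeat tests, so weekly follow-up is presupposed but not instructed.

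None of these restores the prompt notice.

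**Step 4: the revised criterion.** With bilirubin ≥2xULN and ≤35% direct added to the monitoring criterion, the uncovered combinations fall from 24 to 0. In Step 1, only the last line changes, from neither to monitor.

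**The case against.** The strongest objection is that Figure 2 cannot be seen. Its title covers both stopping and increased monitoring, and it may already route this subject. That stands as a limit: the point concerns the wording of Appendix 2, and the protocol as a whole may not be silent.

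Four stronger readings are tempting, and the text does not support them.

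- **That dosing simply continues.** Appendix 2 does not require stopping at 1.9xULN or at 2.2xULN with ≤35% direct. However, Table 3 in Section 5.5.2 may separately lead to holding or reducing the dose for drug-related toxicity.
- **That testing falls back to every 28 days from cycle 2.** Day 1 chemistry is the only fixed schedule left, but the cannot-monitor and persistence rows presuppose weekly tests. What is missing is the explicit instruction.
- **That a subject already being monitored loses oversight when bilirubin crosses 2xULN.** The notice has then been given, and weekly returns run until values resolve, stabilise or return to within baseline. The gap arises only at first presentation.
- **That the step-down line shares the defect.** A subject whose bilirubin stays ≥2xULN does not step down and remains on weekly tests under the same exit conditions. That is conservative.

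The case is also narrow. New or worsening jaundice believed to be liver-related is a symptom that stops treatment, INR is scheduled alongside on-treatment chemistry from Day 7, and cycle 1 chemistry is already about weekly.

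**Conclusion.** The point holds as a minor wording gap in a patient-safety rule. A subject falls outside both tables of Appendix 2 when all of these are true at first presentation: ALT ≥3 to <5xULN for under 4 weeks, bilirubin ≥2xULN, a known direct fraction ≤35%, INR ≤1.5 or unmeasured, no qualifying symptoms, and weekly monitoring possible.

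The clear loss is the medical-monitor notice: within 24 hours below 2xULN, no stated time above it. The explicit weekly-return instruction is not triggered either, although weekly follow-up is implied elsewhere.

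The conclusion assumes that Figure 2 does not already cover the case. If it does, the appendix still needs to be brought into line with it. The documents do not allow an estimate of how many subjects would be affected. No endpoint, sample size or futility rule changes.

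**What to change.** In the increased-monitoring criterion of Appendix 2, replace the bilirubin condition with: bilirubin <2xULN, or bilirubin ≥2xULN with ≤35% direct. Keep the ALT range, the absence of symptoms and the weekly-monitoring condition as they are. Leave the step-down line unchanged, since relaxing it would reduce testing in subjects whose bilirubin is still ≥2xULN. Check that Figure 2 agrees with the revised criterion.

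The cost is one phrase at the next amendment and a look at the figure. In conduct, it adds one prompt notice and weekly liver chemistry for the few subjects who meet the new wording. It creates no new stopping events.
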